## 17.3. Subject Identification, Enrollment, and Screening Logs

The investigator agrees to complete a subject identification and enrollment log to permit easy identification of each subject during and after the study. This document will be reviewed by the sponsor study-site contact for completeness.

The subject identification and enrollment log will be treated as confidential and will be filed by the investigator in the study file. To ensure subject confidentiality, no copy will be made. All reports and communications relating to the study will identify subjects by subject identification and date of birth. Since this a non-randomized study, the date seen and date of birth will be used.

The investigator must also complete a subject screening log, which reports on all subjects who were seen to determine eligibility for inclusion in the study.

### 17.4. Source Documentation

At a minimum, source documents consistent in the type and level of detail with that commonly recorded at the study site as a basis for standard medical care must be available for the following: subject identification, eligibility, and study identification; study discussion and date of signed informed consent; dates of visits; results of safety and efficacy parameters as required by the protocol; record of all adverse events and follow-up of adverse events; concomitant medication; drug receipt/dispensing/return records; study drug administration information; and date of study completion and reason for early discontinuation of study drug or withdrawal from the study, if applicable.

The author of an entry in the source documents should be identifiable.

Specific details required as source data for the study and source data collection methods will be reviewed with the investigator before the study and will be described in the monitoring guidelines (or other equivalent document).

The following data will be recorded directly into the CRF and will be considered source data

- Blood pressure and pulse/heart rate
- Height and weight
- Details of physical examination

## • PRO (Patient Reported Outcomes)

The minimum source documentation requirements for Section 4.1, Inclusion Criteria and Section 4.2, Exclusion Criteria that specify a need for documented medical history are as follows:

- Referral letter from treating physician or
- Complete history of medical notes at the site
- Discharge summaries

Inclusion and exclusion criteria not requiring documented medical history must be verified at a minimum by subject interview or other protocol required assessment (eg, physical examination, laboratory assessment) and documented in the source documents.

If the electronic source system is utilized, references made to the CRF in the protocol include the electronic source system but information collected through the electronic source system may not be limited to that found in the CRF. Data in this system may be considered source documentation.

## 17.5. Case Report Form Completion

Case report forms are prepared and provided by the sponsor for each subject in electronic format. All CRF entries, corrections, and alterations must be made by the investigator or authorized study-site personnel. The investigator must verify that all data entries in the CRF are accurate and correct.

The study data will be transcribed by study-site personnel from the source documents onto an electronic CRF, if applicable. Study-specific data will be transmitted in a secure manner to the sponsor

All subjective measurements (e.g., FACIT Fatigue instrument, EORTC-QLQ-C30) will be completed by the same individual who made the initial baseline determinations whenever possible

If necessary, queries will be generated in the eDC tool. If corrections to a CRF are needed after the initial entry into the CRF, this can be done in either of the following ways:

- Investigator and study-site personnel can make corrections in the eDC tool at their own initiative or as a response to an auto query (generated by the eDC tool).
- Sponsor or sponsor delegate can generate a query for resolution by the investigator and study-site personnel.

# 17.6. Data Quality Assurance/Quality Control

Steps to be taken to ensure the accuracy and reliability of data include the selection of qualified investigators and appropriate study sites, review of protocol procedures with the investigator and study-site personnel before the study, and periodic monitoring visits by the sponsor Written instructions will be provided for collection, handling, storage, and shipment of samples.

The sponsor will review CRF for accuracy and completeness during on-site monitoring visits and after transmission to the sponsor; any discrepancies will be resolved with the investigator or designee, as appropriate. After upload of the data into the study database they will be verified for accuracy and consistency with the data sources.

### 17.7. Record Retention

In compliance with the ICH/GCP guidelines, the investigator/institution will maintain all CRF and all source documents that support the data collected from each subject, as well as all study documents as specified in ICH/GCP Section 8, Essential Documents for the Conduct of a Clinical Trial, and all study documents as specified by the applicable regulatory requirement(s). The investigator/institution will take measures to prevent accidental or premature destruction of these documents.

Essential documents must be retained until at least 2 years after the last approval of a marketing application in an ICH region and until there are no pending or contemplated marketing applications in an ICH region or until at least 2 years have elapsed since the formal discontinuation of clinical development of the investigational product. These documents will be retained for a longer period if required by the applicable regulatory requirements or by an agreement with the sponsor. It is the responsibility of the sponsor to inform the investigator/institution as to when these documents no longer need to be retained.

If the responsible investigator retires, relocates, or for other reasons withdraws from the responsibility of keeping the study records, custody must be transferred to a person who will accept the responsibility. The sponsor must be notified in writing of the name and address of the new custodian. Under no circumstance shall the investigator relocate or dispose of any study documents before having obtained written approval from the sponsor.

If it becomes necessary for the sponsor or the appropriate regulatory authority to review any documentation relating to this study, the investigator/institution must permit access to such reports.

## 17.8. Monitoring

The sponsor will perform on-site monitoring visits as frequently as necessary. The monitor will record dates of the visits in a study site visit log that will be kept at the study site. The first post-initiation visit will be made as soon as possible after enrollment has begun. At these visits, the monitor will compare the data entered into the CRF with the source documents (eg, hospital/clinic/physician's office medical records).

The nature and location of all source documents will be identified to ensure that all sources of original data required to complete the CRF are known to the sponsor and study-site personnel and are accessible for verification by the sponsor study-site contact. If electronic records are maintained at the study site, the method of verification must be discussed with the study-site personnel.

Direct access to source documents (medical records) must be allowed for the purpose of verifying that the recorded data are consistent with the original source data. Findings from this review will

be discussed with the study-site personnel. The sponsor expects that, during monitoring visits, the relevant study-site personnel will be available, the source documents will be accessible, and a suitable environment will be provided for review of study-related documents. The monitor will meet with the investigator on a regular basis during the study to provide feedback on the study conduct.

In addition to on-site monitoring visits, remote contacts can occur. It is expected that during these remote contacts, study-site personnel will be available to provide an update on the progress of the study at the site.

## 17.9. Study Completion/Termination

## 17.9.1. Study Completion/End of Treatment

The study is considered completed with the last visit assessment for the last participating patient in the study. The final data from the study site will be sent to the sponsor (or designee) after completion of the final patient visit assessment at that participating site, in the time frame specified in the Clinical Trial Agreement.

### 17.9.2. Study Termination

The sponsor reserves the right to close the study site or terminate the study at any time for any reason at the sole discretion of the sponsor. Study sites will be closed upon study completion. A study site is considered closed when all required documents and study supplies have been collected and a study-site closure visit has been performed.

The investigator may initiate study-site closure at any time, provided there is reasonable cause and sufficient notice is given in advance of the intended termination.

Reasons for the early closure of a study site by the sponsor or investigator may include but are not limited to:

- Failure of the investigator to comply with the protocol, the requirements of the IEC/IRB or local health authorities, the sponsor's procedures, or GCP guidelines
- Inadequate recruitment of subjects by the investigator

### 17.10. On-Site Audits

Representatives of the sponsor's clinical quality assurance department may visit the study site at any time during or after completion of the study to conduct an audit of the study in compliance with regulatory guidelines and company policy. These audits will require access to all study records, including source documents, for inspection. Subject privacy must, however, be respected. The investigator and study-site personnel are responsible for being present and available for consultation during routinely scheduled study-site audit visits conducted by the sponsor or its designees.

Similar auditing procedures may also be conducted by agents of any regulatory body, either as part of a national GCP compliance program or to review the results of this study in support of a

regulatory submission. The investigator should immediately notify the sponsor if he or she has been contacted by a regulatory agency concerning an upcoming inspection.

### 17.11. Use of Information and Publication

All information, including but not limited to information regarding ibrutinib or the sponsor's operations (eg, patent application, formulas, manufacturing processes, basic scientific data, prior clinical data, formulation information) supplied by the sponsor to the investigator and not previously published, and any data, including research data, generated as a result of this study, are considered confidential and remain the sole property of the sponsor. The investigator agrees to maintain this information in confidence and use this information only to accomplish this study, and will not use it for other purposes without the sponsor's prior written consent.

The investigator understands that the information developed in the study will be used by the sponsor in connection with the continued development of ibrutinib, and thus may be disclosed as required to other clinical investigators or regulatory agencies. To permit the information derived from the clinical studies to be used, the investigator is obligated to provide the sponsor with all data obtained in the study.

The results of the study will be reported in a Clinical Study Report generated by the sponsor and will contain data from all study sites that participated in the study as per protocol. Recruitment performance or specific expertise related to the nature and the key assessment parameters of the study will be used to determine a coordinating investigator. Study subject identifiers will not be used in publication of results. Any work created in connection with performance of the study and contained in the data that can benefit from copyright protection (except any publication by the investigator as provided for below) shall be the property of the sponsor as author and owner of copyright in such work.

Consistent with Good Publication Practices and International Committee of Medical Journal Editors guidelines, the sponsor shall have the right to publish such primary (multicenter) data and information without approval from the investigator. The investigator has the right to publish study site-specific data after the primary data are published. If an investigator wishes to publish information from the study, a copy of the manuscript must be provided to the sponsor for review at least 60 days before submission for publication or presentation. Expedited reviews will be arranged for abstracts, poster presentations, or other materials. If requested by the sponsor in writing, the investigator will withhold such publication for up to an additional 60 days to allow for filing of a patent application. In the event that issues arise regarding scientific integrity or regulatory compliance, the sponsor will review these issues with the investigator. The sponsor will not mandate modifications to scientific content and does not have the right to suppress information. Secondary results generally should not be published before the primary endpoints of a study have been published. Similarly, investigators will recognize the integrity of a multicenter study by not submitting for publication data derived from the individual study site until the combined results from the completed study have been submitted for publication, within 12 months of the availability of the final data (tables, listings, graphs), or the sponsor confirms there will be no multicenter study publication. Authorship of publications resulting from this study will be based on the guidelines

on authorship, such as those described in the Uniform Requirements for Manuscripts Submitted to Biomedical Journals, which state that the named authors must have made a significant contribution to the design of the study or analysis and interpretation of the data, provided critical review of the paper, and given final approval of the final version.

### Registration of Clinical Studies and Disclosure of Results

[figure not shown]
The sponsor will register and disclose the existence of and the results of clinical studies as required by law.

# ATTACHMENTS

Please go on to the next page

© Copyright 1995 EORTC Quality of Life Group. All rights reserved. Version 3.0

O Attachment 2: Functional Assessment of Chronic Illness Therapy-Fatigue FACIT Fatigue Scale (Version 4)

	, , , , , , , , , , , , , , , , , , , ,
CCI	
English (Universal)	16 November
200	7
© Copyright 1987, 1997; FACIT.org. All rights reserved.	Page 1
of	1

### **Attachment 3: Dose Modifications for Adverse Reactions**

ImbruvicaTM therapy should be withheld for any new onset or worsening Grade 2 cardiac failure, Grade  $\geq$  3 non hematological toxicities, Grade 3 or greater neutropenia with infection or fever, or Grade 4 hematological toxicities.

Once the symptoms of the toxicity have resolved to Grade 1 or baseline (recovery), resume IMBRUVICA therapy at the recommended dose as per the tables below.

Table 1: Recommended dose modifications for events of cardiac failure or cardiac arrhythmias:

Events	Toxicity occurrence	MCL/MZL dose modification after recovery Starting Dose 560 mg/day	CLL/SLL/WM/cGVHD dose modification after recovery Starting Dose 420 mg/day
	First	Restart at 420 mg daily	Restart at 280 mg daily
Grade 2 cardiac failure	Second	Restart at 280 mg daily	Restart at 140 mg daily
	Third	Discontinue Imbruvica™	
Grade 3 cardiac	First	Restart at 420 mg daily †	Restart at 280 mg daily †
arrhythmias	Second	Discontinue Imbruvica™	
Grade 3 or 4 cardiac failure Grade 4 cardiac arrhythmias	First	Discontinue Imbruvica™	

<sup>† Evaluate the benefit-risk before resuming treatment.

Table 2: Recommended dose modifications for non-cardiac events:

Events	Toxicity occurrence	MCL/MZL dose modification after recovery Starting Dose 560 mg/day	CLL/SLL/WM/cGVHD dose modification after recovery Starting Dose 420 mg/day
Grade 3 or 4 non-hematological toxicities	First*	Restart at 560 mg daily	Restart at 420 mg daily
	Second	Restart at 420 mg daily	Restart at 280 mg daily
Grade 3 or 4 neutropenia with	Third	Restart at 280 mg daily	Restart at 140 mg daily
infection or fever  Grade 4 hematological toxicities	Fourth	Discontinue Imbruvica™	

\*When resuming treatment, restart at the same or lower dose based on benefit-risk evaluation. If the toxicity reoccurs, reduce daily dose by 140 mg.

#### Summary of updated dosage modification recommendations:

- For patients experiencing Grade 2 cardiac failure, resume ImbruvicaTM treatment at a lower dose (i.e., reduce daily dose by 140 mg).
- For patients experiencing Grade 3 cardiac arrhythmias, evaluate the benefit-risk, and if resuming ImbruvicaTM treatment, re-start at a lower dose (i.e., reduce daily dose by 140 mg).

- For patients experiencing Grade 3 or 4 cardiac failure or Grade 4 cardiac arrhythmias, discontinue ImbruvicaTM at first occurrence.
- For patients experiencing Grade 3 or 4 non-cardiac events, when resuming ImbruvicaTM treatment, evaluate benefit-risk and re-start at the same or lower dose (i.e., reduce daily dose by 140 mg).

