## 9.2. Safety Evaluations

Any clinically relevant changes occurring during the study will be recorded in the Adverse Event section of the CRF. Any clinically significant abnormalities persisting at the end of the study or at discontinuation will be followed by the participating physician until resolution or until a clinically stable outcome is reached.

All non-haematological AEs including laboratory AEs and AEs leading to dose reductions or discontinuation will be graded and reported according to the National Cancer Institute Common Terminology Criteria for Adverse Events (NCI-CTCAE), Version 4.0. All haematological AEs will be graded and reported according to the IWCLL 2008 criteria for grading of haematological toxicities in CLL studies. The study will include the evaluations of safety and tolerability according to the time points provided in the TIME AND EVENTS SCHEDULE.

Safety assessments will be based on medical review of adverse event reports and the results of vital sign measurements, physical examinations, clinical laboratory tests, ECOG performance status, and other safety evaluations at specified time points as described in the Time and Events Schedules

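### Attachment 3 gives inconsistent instructions for restarting ibrutinib after a repeat non-cardiac event

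*Protocol*

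**What the plan says.** Amendment 1 (20-Oct-2022) added Attachment 3. The Synopsis, Section 1.2 and Section 6 send sites to it alongside the locally approved prescribing information. Three parts of the attachment deal with restarting after a non-cardiac event.

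- **Table 2, rows.** The rows run by occurrence. The first entry for MCL is "Restart at 560 mg daily", and the matching CLL entry is 420 mg. The second row gives 420 mg (MCL) or 280 mg (CLL), and the third gives 280 mg or 140 mg. At the fourth, treatment is discontinued.
- **Table 2, footnote.** The mark sits on the first-occurrence row only. It reads: "When resuming treatment, restart at the same or lower dose based on benefit-risk evaluation. If the toxicity reoccurs, reduce daily dose by 140 mg".
- **Summary bullet.** It begins "For patients experiencing Grade 3 or 4 non-cardiac events, when resuming" and goes on to "evaluate benefit-risk and re-start at the same or lower dose (i.e., reduce daily dose by 140 mg". No occurrence number and no stopping step are given. The bullet directly above it, on the more severe cardiac events, does name an occurrence: "at first occurrence".

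The introductory text of Attachment 3 directs that, after recovery, therapy be resumed according to the tables that follow it.

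**The concern.** A site that has to act on a second, third or fourth non-cardiac event can find different answers in different parts of one attachment. The bullet, taken on its own words, leaves open a same-dose restart at any occurrence, whereas the table does not. A site that reads Table 2 alone can also reach two different doses at the second event, depending on whether it follows the row or the footnote.

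This is safety text in a trial whose primary objective is safety. Different handling of the same event would also enter the reported results. SAP Section 4.4 summarises subjects with dose reductions or adjustments, and Section 6.1 tabulates TEAEs leading to discontinuation of study agent. Neither output could separate differences between sites in how they read Attachment 3 from differences in how subjects tolerated the drug.

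**Working it through.** No sample-size or error-rate formula applies. The check follows each instruction through successive occurrences and compares the result with the Table 2 rows.

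**Inputs (Attachment 3).** Starting dose is 560 mg/day (MCL) or 420 mg/day (CLL). The reduction step is 140 mg. The footnote does not say how much lower a lower first restart is, so I take one 140 mg step, as the summary bullet does.

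**Step 1: reproduce the table.** Restart at the starting dose after the first event, then subtract 140 mg at each recurrence.

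- MCL: 560; 560 − 140 = 420; 420 − 140 = 280.
- CLL: 420; 420 − 140 = 280; 280 − 140 = 140.

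These match the first three rows. The fourth row is a separate instruction to stop. Rows and footnote therefore agree for the first three occurrences when the first restart is at the same dose.

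**Step 2: use the footnote's other option, a lower first restart.**

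- MCL: the first restart is 560 − 140 = 420. On recurrence the footnote gives 420 − 140 = 280. The second row gives 420.
- CLL: the first restart is 420 − 140 = 280. On recurrence the footnote gives 280 − 140 = 140. The second row gives 280.

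In both diseases the row repeats the dose already being taken, while the footnote calls for 140 mg less. The mismatch carries to the third occurrence. For MCL the footnote gives 280 − 140 = 140 against a row of 280. For CLL it gives 140 − 140 = 0 against a row of 140.

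**Step 3: apply the summary bullet literally at every occurrence** (stay at the current dose or go down 140 mg, counting only doses above zero).

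| Occurrence | MCL, bullet permits (mg) | MCL, Table 2 row | CLL, bullet permits (mg) | CLL, Table 2 row |
|---|---|---|---|---|
| 1 | 560, 420 | 560 (footnote: same or lower) | 420, 280 | 420 (footnote: same or lower) |
| 2 | 560, 420, 280 | 420 | 420, 280, 140 | 280 |
| 3 | 560, 420, 280, 140 | 280 | 420, 280, 140 | 140 |
| 4 | 560, 420, 280, 140 | discontinue | 420, 280, 140 | discontinue |

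Bullet and table agree at the first occurrence once the footnote is included. They part at the second, and by the fourth one permits a restart where the other stops treatment.

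**The case against.** The best defence is that the tables govern. Attachment 3 says to resume according to them, and the later list is labelled a summary. Other bullets in that list are abbreviated too: the Grade 2 cardiac failure bullet leaves out discontinuation at the third event, and the Grade 3 arrhythmia bullet leaves out discontinuation at the second. On this view the non-cardiac bullet merely restates the first step of Table 2. That is a fair reading and it softens the first inconsistency. It does not remove it, because the bullet does not say that it describes the first occurrence only.

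The defence does not reach the second inconsistency, which lies inside Table 2. One could say the rows assume a same-dose first restart, but the table does not state that, and its footnote expressly allows the alternative.

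Two further points stand. Attachment 3 is read with the local prescribing information, which is not among the documents, so actual divergence between sites cannot be shown. And the effect on the analysis is limited: the primary endpoint is the number and type of TEAEs, and dose reductions are reported descriptively, with dates and reasons listed.

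A reader might also infer two wider faults that the documents do not support.

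- **Scope.** The bullet might seem to cover every Grade 3 haematological event, whereas the withholding rule lists "Grade 3 or greater neutropenia with infection or fever, or Grade 4 hematological toxicities". But the bullet speaks of resuming, which presupposes that treatment was withheld under that rule.
- **Grading scale.** Attachment 3 names no scale for its haematological grades, but Section 9.2 does: "All haematological AEs will be graded and reported according to the IWCLL 2008 criteria". The Synopsis and Section 8 say the same. The NCI-CTCAE clause on AEs leading to dose reduction sits in a sentence about non-haematological AEs. Neither scale's cut-offs are reproduced, so the documents cannot show that one cytopenia would be graded two ways.

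**Conclusion.** Attachment 3 is inconsistent on restarting after a repeat non-cardiac event, in two ways. The summary bullet, read literally, departs from Table 2 from the second occurrence on; this may be loose shorthand. The footnote and the second-occurrence row give doses 140 mg apart whenever the first restart was one step lower; this cannot be read away from the text supplied. The second result rests only on taking the lower restart as one 140 mg step.

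How many subjects are affected cannot be derived. A reader might multiply the pooled Grade 3 or 4 rate in Section 1.2 (49.3%) by 75 to get about 37 and then apply a repeat rate. That rate counts all Grade 3 or 4 events, including cardiac events, which fall under Table 1, and uncomplicated Grade 3 cytopenias, which trigger nothing in Table 2. The documents give no repeat rate. They also do not show how much treatment took place after Attachment 3 was introduced.

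The fault is one of wording, but in safety instructions that sites are told to follow, so it should be corrected.

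**What to change.** The sponsor should reconcile three pieces of text in Attachment 3 on occurrence number: the non-cardiac summary bullet, the Table 2 footnote and the Table 2 rows.

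- The bullet should state which occurrence it describes. If the tables are meant to govern, the summary should say so.
- The second and third rows should be made consistent with the footnote for a subject whose first restart was at a lower dose.

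Which dose rule is right is for the sponsor to settle, and this review takes no position on it. A cross-reference from Attachment 3 to the grading rule in Section 9.2 would be a convenience only.

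The cost is a few lines in one attachment and a clarification letter to sites. If the correction changes what sites do, the ethics committee approval requirement for amendments in Section 17.1 applies. No change to the SAP is needed.
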